Venous blood samples will be drawn to measure clozapine levels once during the titration phase (Day 14), or more often if needed during titration for clinical purposes, monthly during the 6-month clozapine treatment phase, and at the conclusion of the study. Levels will be obtained prior to the administration of the morning dose of clozapine. Samples will be analyzed using High Performance Liquid Chromatography (HPLC). Clozapine levels (clozapine, norclozapine) are sent out to LabCorp at the MPRC and Howard University site. At the MPRC these may also be sent to Saladax Biomedical, Inc, Bethlehem PA for immunoassay. HPLC equipment is budgeted for the Nigerian site so that all laboratory tests are done in the same lab to ensure standardization and QC. The purpose of the blood levels are 1) to ensure clozapine is being taken and 2) examine relationship of clozapine levels to ANC levels. Lab values that are considered to be abnormal may be repeated to verify accuracy. A corresponding capillary draw will occur at baseline, approximately week 4 and 8 to confirm it matches venous blood levels. This is optional and only offered at MPRC site with capillary tubes.

Other Laboratory and Metabolic Monitoring:

A chemistry panel (liver enzymes, BUN, creatinine, electrolytes, thyroid), and metabolic profile (lipids, fasting blood glucose) will be drawn at baseline and repeated monthly. All laboratory values outside normal ranges will be discussed and addressed with the medically accountable physician and clinical team at each site. A determination of

appropriate diagnostic procedures and/or follow up treatment will be made by the medically accountable physician. Lab values that are considered to be abnormal may be repeated to verify accuracy. We also will be collecting existing lab values if possible and will request only with patient permission for previous records. Cytokines labs will be drawn prior to the start of clozapine, and at the middle and endpoint of the clozapine trial.

INFECTION MONITORING:

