- The DNA will be shipped from Nigeria to the MPRC using either Oragene DNA kits or Whatman FTA Elute Micro Cards. DNA is relatively stable and currently DNA is being shipped on other collaborative grants without problems.

CLOZAPINE DOSING:

- Following consent and prior to initiation of clozapine, eligible patients will have weekly WBC/ANC. During this period, patients will be registered with the clozapine manufacturer and other medications will be appropriately titrated. Patients may be inpatients or outpatients.
- Clozapine will be recommended to be prescribed twice daily (other regimens permitted). The dose will be titrated within a range of 200-900 mg daily. *We do permit* individualized dosing, as occurrence of neutropenia and agranulocytosis is not clozapine dose-related. See recommended titration schedule below. If a patient has not received clozapine for two days or more he/she will need to have their clozapine initial dose be reinstated.

Recommended Clozapine Titration Schedule (3 week)

This is only a recommended titration schedule. This can be modified if necessary.

Day 1:	12.5 mg BID (1/2 of the 25 mg tablet)	
Day 2:	25 mg AM, 0mg HS	
Day 3:	25 mg AM, 25 mg HS	Extra visit, vitals, side effect and safety check
Day 4:	25 mg AM, 50 mg HS	
Day 5:	50 mg AM, 50 mg HS	
Day 6:	50 mg AM, 75mg HS	
Day 7:	50mg AM, 100 mg HS	Visit, vitals, side effect and safety, WBC
Day 8:	50mg AM, 100mg HS	
Day 9:	100 mg AM, 100 mg HS	
Day 10:	100 mg AM, 100 mg HS	
Day 11:	50 mg AM, 200 mg HS	
Day 12:	50 mg AM, 200 mg HS	
Day 13:	100 mg AM, 200 mg HS	
Day 14:	100 mg AM, 200 mg HS	clozapine blood level will be drawn, visit, vitals, side effect and safety, WBC
Day 15:	125 mg AM, 200 mg HS	
Day 16:	125 mg AM, 200 mg HS	
Day 17:	150 mg AM, 200 mg HS	
Day 18:	150 mg AM, 200 mg HS	
Day 19:	175 mg AM, 200 mg HS	
Day 20:	175 mg AM, 200 mg HS	
Day 21:	200 mg AM, 200 mg HS	Visit, vitals, side effect and safety, WBC

The white blood cell count level is not related to the dose of the medication. The dose throughout the study will not be altered based on white blood cell counts, but if the white blood cell counts fall lower than the established monitoring parameters for each patient the patient may be discontinued from treatment.

MONITORING GUIDELINES:

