 - viii. Only with compelling clinical circumstances should you consider starting granulocyte colony stimulating factors. In this case either filgrastim daily at 480 mcg subcutaneously (SQ) daily until ANC is $> 1000 /\text{mm}^3$ or a single dose of pegfilgrastim 6 mg SQ. The study nursing staff will arrange for seeing the patient for injections. This will be determined with hematology consult ONLY. These subjects will have daily contact by phone with a research nurse. Growth factor use can be associated with fever so use only if directed by hematology.
 - ix. For all subjects whose ANC does not increase above $500 /\text{mm}^3$ 20 days after last dose of clozapine or hematology recommendation, there may be consideration of bone marrow aspirate and biopsy.
6. If a participant falls below $500/\text{mm}^3$ he/she will likely be discontinued from the study. In this case, the research team will contact the clinical teams to check on the status of the patient and the outcomes of the patient event will be recorded, however the participant will not continue to with study visits and assessments. Only if a participant is seen by the ER, admitted for infection symptoms or receives filgrastim or pegfilgrastim this will be documented as a serious adverse event (SAE) and information sent to all regulatory bodies.
7. If participant is rechallenged with clozapine, resume treatment as a new patient monitoring level once ANC $\geq 1000/\text{mm}^3$ or at least patient's known baseline.

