We will also collect data on WBC, ANC and demographic information on people previously treated in Maryland on a waiver system. Their data is available in clinical charts at Spring Grove Hospital and will only collect with approval from the hospital and the Spring Grove Research Committee. These patients will not be eligible to reenroll in this study but the data will be available to add to the study as it will help decrease the final sample size needed to enroll in the study. We will link this data from another study approval where a waiver of informed consent has been granted to study antipsychotic use (HP-00040084).

PRIMARY OUTCOME VARIABLES:

The primary outcomes are to measure ANC levels, side effects and patient safety.

STATISTICAL ANALYSES:

Analysis of Effect of clozapine on WBC and ANC levels: We will characterize variation of WBC and ANC levels in participants by *DARC* null genotype. We anticipate 212+ AA participants with BEN who are homozygous for the *DARC* null allele who will be the focus of this analysis, with other participants with BEN to be examined in a separate analysis. We will compute within-patient means and standard deviations of weekly WBC and ANC by three months intervals, starting with the three-month pre-treatment phase, and continuing for the six-months of follow-up on clozapine treatment, and observe the frequency of ANC values observed that exceed specific levels of concern (e.g. <500, <700, <1000 cells/mm³). We will estimate the change from baseline in overall average WBC and ANC during each three month interval after initiation of clozapine, and assess whether these change with time using a mixed model for repeated measures ANCOVA, controlling for baseline. Frequency of other events of concern (serious infection, need for treatment for very low ANC) will also be reported. We will also perform analyses of effects of mean participant pre-treatment ANC, clozapine dose and clozapine blood level on mean ANC during clozapine treatment and ANC<500 cells /mm³ during clozapine treatment, using linear and logistic regression. To date all published work and US guidelines are based on non-BEN samples and not specific to schizophrenia patients.

For the study when we report the results we will evaluate a subgroup of people with a history of ANC < 1500 cells/mm³

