Risk of Agranulocytosis - Analysis and Power: The analysis of this aim will resemble that for an equivalence trial comparing effectiveness of two treatments, only instead we will be comparing safety outcomes between two populations (patients with and without BEN), using an extremely large historic control group rather than newly recruited controls. We will compare estimated risk of agranulocytosis in our study to a large historic cohort study estimating risk of agranulocytosis in non-BEN patients followed according to current FDA guidelines during clozapine treatment. In a report on 11,555 clozapine-treated patients followed for agranulocytosis. There is an incidence rate of 0.9% at one year (upper 95% CI 0.99), with over 80% of cases observed within the first three months, from which we conclude that our planned six-month follow-up on clozapine is adequate to cover the period of highest risk. Some participants will discontinue clozapine prior to conclusion of the six-month treatment phase. In the CATIE trial, 15% of participants assigned to clozapine had discontinued treatment by six months. To adjust for missing data due to dropout, we will use the Kaplan-Meier method for censored survival data to calculate a point estimate of the proportion of cases of agranulocytosis by six months. However, we anticipate few if any cases of agranulocytosis in our cohort, so that usual methods of calculating a CI for the percent without an event at six months which rely on large sample estimators may not work well. Accordingly, we will also use all clozapine-treated cases, ignoring variation in follow-up on clozapine, to calculate a binomial approximation for an upper 95% confidence limit for the risk, r , of agranulocytosis during the first six-months on by solving the equation $0.95 = 1 - \sum_{j=0}^k \frac{n!}{j!(n-j)!} r^j (1-r)^{n-j}$, where r is probability (risk) of agranulocytosis, n is the total number of participants, k is the number of cases of agranulocytosis, and the summation runs from $j=0$ to k . If no cases are observed, this reduces to $0.05 = (1-r)^n$; we will use similar a similar formula to calculate the lower confidence limit (LCL); if the LCL does not include the risk level in the historic control cohort, we would reject strict equivalence of risk. With $n=212$ *DARC* null homozygous participants, zero cases observed would give an upper limit on the risk of 1.4%, approximately 1.4 x the estimated risk of agranulocytosis in non-BEN patients reported in a U.S. cohort of 11,555 patients treated with clozapine. Thus, we will not be able to demonstrate complete equivalence to the risk of

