The major risks of the study are the risk for infection and neutropenia. Based on all existing data, genetic testing, use in chemotherapy trials and our pilot test cases, we don't expect subject ANC levels to drop below 700 cells/mm³, however, a number of patients may fluctuate below 1000 cells/mm³ throughout the study. We are paying careful attention to the risk of infection and neutropenia. As listed in the methods we have a careful plan for ANC and infection monitoring. In rare instances a bone marrow biopsy or aspiration may be needed.

- iii. Risk related to participating in research interviews (Research Risk)

The risk from research interviews is minimal and relatively uncommon. During assessments participants may be uncomfortable discussing their smoking habits or mental health history and treatments. Participants may become frustrated and tense when they encounter difficulty when completing these measures. Careful planning and observation of the participant's response to these sessions will allow the testing to be completed with a minimum of discomfort. Participants will take breaks when necessary to help alleviate any discomfort. All interviewers are trained to recognize signs of distress or anxiety. The participant will be reminded that they can refuse to answer any question that makes them uncomfortable and may take breaks whenever they are needed. There is a slight risk of breach of confidentiality. All data will be coded with an ID number that is unique. All data including information from chart reviews, therapist reports and laboratory results will be labeled by ID only. Only members

of the study team will have access to the link between the ID and participant's name. Data containing names and personal information will never be included in published materials.

iv. Other risks.

Blood draws may be associated with tenderness or bruising. A cream can be used to reduce the pain or discomfort from inserting the needle. The cream itself may cause the skin to become pale, red, or swollen. Inserting the needle may cause dizziness or fainting. Infection is rare, because sterile methods are used. The total amount of blood taken during the study is about half of the blood taken in one blood donation. This amount of blood is usually replaced by the body without any problems. A rash could appear at the site of the EKG pads.

CONFIDENTIALITY AND PROTECTIONS AGAINST RISK:

Protections against Therapeutic and Research Risk

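### The logistic regression of ANC<500 expects about two events, has no sparse-event rule and defines no dose or blood-level window

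*Combined protocol and SAP*

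**What the plan says.** Under Statistical Analyses (Analysis of Effect of clozapine on WBC and ANC levels), the plan will study "effects of mean participant pre-treatment ANC, clozapine dose and clozapine blood level on mean ANC during clozapine treatment and ANC<500" cells/mm³ during treatment, by linear and logistic regression. It does not say whether the three predictors enter together, which test is used, what happens with few or no events, or over what period dose and blood level are summarised.

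The next section, Risk of Agranulocytosis - Analysis and Power, states that "we anticipate few if any cases of agranulocytosis in our cohort". It warns that the usual interval methods that "rely on large sample estimators may not work well", and adds a binomial limit for the risk estimate only. Risks and Discomforts (item ii) adds that the investigators do not "expect subject ANC levels to drop below 700" cells/mm³.

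On timing, the historic cohort is described "with over 80% of cases observed within the first three months". Clozapine Dosing gives a "Recommended Clozapine Titration Schedule (3 week") that rises from 25 to 400 mg/day. The Clozapine Blood Levels section schedules venous sampling "once during the titration phase (Day 14"), then monthly, and names the relation of levels to ANC as one purpose. It does not say which level enters a model.

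**The concern.** There are two gaps, both confined to the ANC<500 half of that sentence.

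**Sparse events.** The plan recognises the problem for the risk estimate and leaves the regression, which faces the same event count, unprotected. With zero events there is no model, and with one to three the fit is fragile and the intervals are very wide. A null result would seem to confirm the statement under Clozapine Dosing that neutropenia is not dose-related, although the model could hardly have shown otherwise.

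**Exposure window.** ANC<500 interrupts therapy, so a case's dose record stops at the event. If events come early and dose is averaged over each person's time on drug, a case is averaged largely over titration and a completer over 26 weeks. That pushes the apparent dose effect towards higher doses looking protective when dose has no effect. Unlike the first gap, more events do not cure this.

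**Working it through.** **The plan's own figure.** With zero cases, 0.05 = (1-r)^212 gives r = 1 - 0.05^(1/212) = 1.40%, which reproduces the stated 1.4%. The plan gives no event count or power for the regression.

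**Expected events.** Inputs are n = 212 (250 less 15% dropout, 250 × 0.85 = 212.5; also the anticipated number of *DARC*-null homozygotes) and a risk of 0.9% at one year, both from the risk and safety-monitoring text.
- Expected events: 212 × 0.009 = 1.91.
- P(0) = 0.991^212 = 14.7%.
- P(1) = 28.3% and P(2) = 27.1%, so P(≤2) = 70.2%.
- P(≥6) = 1.3%.
- At the 1% quoted in Aim 3: 2.1 events. At an assumed 2%: 4.2. With n = 250 at 0.9%: 2.25.
- Events per predictor, three predictors: 1.91/3 = 0.64.

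**What the model can deliver.** This is a simulation at 0.9% with 2,500 trials per scenario, three standard-normal predictors entered jointly, and a two-sided 5% test. Zero events or non-convergence counts as no usable fit and no rejection. Predictor scale, effect size and joint entry are assumptions.

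| Method | Power, OR 2 per SD | Power, OR 3 per SD |
|---|---|---|
| Maximum likelihood, Wald | 8% | 18% |
| Firth, penalised likelihood ratio | 12% | 27% |

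Maximum likelihood gave no usable fit in 19-23% of trials; about 15 of those points are zero-event trials. At OR 2 the median standard error was 0.777, so the 95% interval spans exp(3.92 × 0.777) = 21-fold. Entering one predictor at a time gives 15-17% unusable fits and power of 10% and 22%.

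**Dose averages.** The printed 21-day schedule sums to 4,700 mg. Holding 400 mg/day afterwards (assumption), mean dose over time on drug is:
- to day 21: 4,700/21 = 224 mg/day
- to day 42: (4,700 + 21 × 400)/42 = 312
- to day 91: (4,700 + 70 × 400)/91 = 359
- to day 182: (4,700 + 161 × 400)/182 = 380

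**Effect on the regression.** This simulation has 212 participants, two cases unrelated to dose, final dose Normal(400, SD 100) mg limited to 200-900 mg, and 80% of events spread evenly over the early period stated, with 20% on days 92-182. Dose enters alone, as the time-on-drug mean. The SD and the spread within three months are assumptions.

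| Early events on days | Non-cases stopping early | Spurious OR per SD (about) | False positives, Firth likelihood ratio |
|---|---|---|---|
| 1-91 | none | 0.45 | 27-30% |
| 1-91 | 15% | 0.50 | 22% |
| 22-91 | none | 0.62 | 8% |
| 22-91 | 15% | 0.7 | 5% |

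In the first row, maximum likelihood with a Wald test gives about 14%; in the last it gives 4%. The first row also depends on the dose spread: 18% at SD 150 mg and 49% at SD 50 mg. Comparing each case with participants still on drug on the same treatment day gives 4-6%.

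**Blood level.** The direction is less certain. If early events are even over days 1-91, 0.8 × 13/91 = 11% of cases precede the day-14 level. Against that, Infection Monitoring calls for an extra level during infection because levels can rise.

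**The case against.** The strongest reply is that this is half of one sentence of secondary analysis. ANC<500 frequencies are already to be reported, each agranulocytosis case goes to the DSMB, and the risk estimate has its own binomial limit. On the investigators' expectation there may be no event and so no model. All of that stands and keeps the point modest. It does not supply the missing rule for one to three events.

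The second reply is that the window effect depends on choices the plan has not made. Time-on-drug mean dose is only one reading; target dose, which the event cannot alter, would avoid most of the artefact. The documents place over 80% of cases in three months but do not say they are even from day 1, and the higher false-positive rates need events during titration. This also stands. A reader might infer that a false protective effect of dose is likely, citing the 53% false-positive rate simulated with six cases. Six or more events have a 1.3% probability at the benchmark, so that rate does not describe this trial.

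A reader might also link the regression to a conflict over follow-up. Monitoring Guidelines (ANC<500, item 6) expects likely discontinuation from the study and says "the participant will not continue to with study visits and assessments", while Withdrawal Criteria lets participants who stop clozapine continue monitoring and blood levels. The conflict is real but separate: levels drawn after stopping would not be predictors of ANC<500 during treatment.

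**Conclusion.** The concern holds as a modest point on a secondary analysis. The sparse-event gap is firm: about 1.9 expected events at the plan's benchmark, and still only 4.2 at an assumed 2%. That benchmark is an agranulocytosis rate from non-BEN patients, so single unconfirmed readings below 500 could be more frequent.

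The window gap is firm in direction for time-on-drug mean dose and uncertain in size. With two cases the spurious OR is roughly 0.5-0.65 per SD in the middle scenarios (about 0.45 to 0.7 across the four), and the false-positive rate runs from nominal to about 27-30% at the assumed dose SD of 100 mg. A shift in apparent dose is expected; a false significant finding is only possible.

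The documents do not support saying that the plan overlooks sparse events altogether, or that the main safety estimate is affected. The binomial risk limit and the linear model on mean ANC are untouched.

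**What to change.** 1. List each ANC<500 case with pre-treatment ANC, dose, last scheduled on-drug level and treatment day.
2. Fit no model with zero events. Otherwise replace ordinary logistic regression with Firth regression and a penalised likelihood-ratio interval, one predictor at a time below a pre-stated number of events (for example 10). Label it exploratory and state that a null result is not evidence of no effect.
3. For dose and level, compare each case with participants still on clozapine on the same treatment day, summarised over the same days before the ANC<500 draw. Use only scheduled on-drug levels, and state how a case with no prior level is handled.
4. Keep the linear model on mean ANC.
5. Separately, reconcile Monitoring Guidelines (ANC<500, item 6) with Withdrawal Criteria on whether these participants continue study assessments.

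The cost is analysis-plan wording and modest programming, with no new data. The downside is a little more work for a result that stays exploratory and low in power: with two cases the same-day comparison has about 17% power at OR 2 and 34% at OR 3 per SD, by normal approximation.

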New knowledge is needed to reduce this healthcare disparity and care gap for African-American patients who would otherwise benefit from clozapine treatment. To generate this knowledge, the objectives of the study are:

Aim 1: To study and understand the normal pattern of white blood cell fluctuations in BEN patients. We will study 250, mostly African ancestry, patients to determine the fluctuations of within-participant WBC and ANC (mean, S.D., frequency and duration of episodes of mild, moderate or severe neutropenia), measured weekly over a period of (up to) 6 weeks

Hypothesis:

BEN patients will have lower mean ANC and WBC than normal values reported in the literature. The normal variation in ANC and WBC will create sporadic episodes with ANC below guidelines in BEN patients.

Aim 2: To test to see if people with BEN have a genetic risk that may put them at risk of having a naturally lower WBC count than people who are White. We will establish ANC and WBC patterns in both those with and without the *DARC* allele.

We will also genotype a panel of variants in the human leukocyte antigen (*HLA*) complex gene recently shown to be associated with agranulocytosis in Caucasian patients, to explore the prevalence of co-occurrence of these *HLA* variants and the *DARC* null genotype in BEN patients, which might increase risk of agranulocytosis in AA and SSA participants with BEN. We anticipate that the high risk *HLA* variants will be in very low frequency in the AA and SSA population

*Hypothesis: Patients with the *DARC* null allele genotype will have lower ANC and WBC than people without the *DARC* null allele genotype.*

Aim 3: To test the safety of clozapine treatment in people with BEN. We also will study the normal fluctuations of WBCs and ANCs during 6 months of clozapine treatment. We will study the risk of potential episodes of agranulocytosis or serious infection. We will develop an upper 95% confidence interval for risk of agranulocytosis ($< 500 \text{ cells/mm}^3$), which may be compared to the known 1% agranulocytosis risk in European ancestry populations treated with clozapine. We will also estimate the risk of serious infection in clozapine-treated BEN patients.

Hypothesis 1 (DARC null allele patients):

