The 6-month risk of agranulocytosis in clozapine-treated BEN patients will not differ from reported rates in the literature. In the DARC null allele patients, normal variation in ANCs and WBCs will create sporadic episodes with ANCs below usual U.S. monitoring guidelines ($<1500 \text{ cells/mm}^3$), but not higher rates of agranulocytosis or severe infection. These patients will have lower mean ANC and WBC than patients without the polymorphism, and not have higher rates of agranulocytosis.

Hypothesis 2: (non DARC null allele patients)

BEN patients without the polymorphism will have higher mean ANC than the group with the genetic polymorphism (DARC null alleles), and will be less likely to have episodes with ANCs below usual U.S. monitoring guidelines ($<1500 \text{ cells/mm}^3$). We will evaluate any identifiable causes (e.g., infection) of low ANC in such participants

STUDY PARTICIPANTS:

Inclusion Criteria
Eligible and recommended for clozapine treatment (e.g. treatment resistant schizophrenia, schizoaffective disorder, bipolar disorder, other psychotic disorder, delusional disorder, hostility, other documented rationale)
Male or Female
African Ancestry (African, African-American or African-Caribbean). This population will make up the majority of the study. However, there are cases of BEN in individuals of Middle Eastern, Caucasian, and other ethnicity. We will accept these patients as they may have unknown African ancestry and genotyping will be important. Caucasian subjects will only be recruited if they have a history of an absolute neutrophil count (ANC) $<2500 \text{ cells/mm}^3$ in past 24 months
Age: 18 to 64 years.
Documented ability to sign informed consent. This is a score of $\geq 10/12$ on ESC.
Effective birth control if of child bearing potential

Exclusion Criteria
Pregnancy or lactation
History of myeloproliferative disorder
Uncontrolled seizure disorder
History of paralytic ileus
History of 3 or more successive ANC values below 500 cells/mm^3

Systemic Lupus Erythematosus, Multiple Sclerosis, Hashimoto's Thyroiditis, Sjogren's Syndrome, Grave's Disease*
Medical condition whose pathology or treatment would likely alter the presentation or treatment of schizophrenia or significantly increase the risks associated with the proposed protocol.
Medical condition affecting patient's ability to mount an immune response
Current symptomatic bacterial or viral infection*
Sickle cell anemia
Temperature > 38.0 ° Celsius, 100.4 ° Fahrenheit*

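### The trial's six-month agranulocytosis risk is set against an unconverted one-year historic risk, which understates the excess-risk ratio by up to a factor of 1.25

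*Combined protocol and SAP*

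**What the plan says.** All references are to the combined protocol and SAP.

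- **Trial quantity.** Hypothesis 1 under Aim 3 reads: "The 6-month risk of agranulocytosis in clozapine-treated BEN patients will not differ from reported rates in the literature". In Statistical Analyses, under Risk of Agranulocytosis - Analysis and Power, the Kaplan-Meier method is to "calculate a point estimate of the proportion of cases of agranulocytosis by six months". A binomial upper limit is also planned for the first six months of treatment.
- **Benchmark.** The same section takes its comparator from a cohort of 11,555 clozapine-treated patients: "There is an incidence rate of 0.9% at one year", with an upper confidence limit of 0.99. Aim 3 instead cites a "known 1% agranulocytosis risk in European ancestry populations treated with clozapine" and gives no time horizon.
- **Timing.** The benchmark sentence continues "with over 80% of cases observed within the first three months", and concludes that "our planned six-month follow-up on clozapine is adequate to cover the period of highest risk".
- **Uses of the benchmark.** There are two. With zero cases in 212 participants, the 1.4% upper limit is described as roughly 1.4 times the cohort's risk. Strict equivalence is to be rejected if the trial's lower confidence limit excludes the cohort's risk.
- **Stated limitation.** The section accepts that complete equivalence cannot be shown and claims only to bound the excess risk.

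**The concern.** The two sides of the comparison cover different lengths of time. A one-year cumulative risk includes any historic cases from months 7 to 12, and the trial's six-month risk has no counterpart to those. The remark on early cases is a sound reason for following patients for six months, but it does not turn a one-year risk into a six-month one, and no conversion is planned elsewhere.

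The error can run in one direction only. A benchmark that is too high makes patients with BEN look safer relative to the historic cohort. The excess-risk ratio is the figure by which the protocol argues that further clinical experience would be justified, and the sponsor hopes the data will inform treatment guidelines. That ratio should compare equal time windows.

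**Working it through.** **Inputs** (Risk of Agranulocytosis - Analysis and Power; Table 1 under Safety Monitoring): n = 212, from 250 × 0.85 = 212.5; historic risk 0.9% at one year; more than 80% of historic cases by month 3; zero-case formula 0.05 = (1 − r)^n.

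**1. Reproduce the plan's upper limit.** r = 1 − 0.05^(1/212) = 1.403%, which matches the stated 1.4%. The limit is one-sided; putting 0.025 in place of 0.05 gives 1.725%.

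**2. Reproduce the plan's ratio.** 1.403 / 1.00 = 1.40 and 1.403 / 0.99 = 1.42, but 1.403 / 0.90 = 1.56. The stated ratio of about 1.4 therefore needs a benchmark near 1%, not the 0.9% given for the cohort. This discrepancy has nothing to do with follow-up length.

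**3. Bound the six-month benchmark.**

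- Ceiling: no historic cases after month 6, giving 0.90%.
- Floor: exactly 80% of cases by month 3 and none in months 4 to 6, giving 0.80 × 0.9% = 0.72%.
- Illustration: exactly 80% by month 3 and the rest spread evenly over months 4 to 12, giving 0.9% × (0.80 + 0.20 × 3/9) = 0.78%.

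**4. Ratio of the 1.403% limit to each benchmark.**

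| Benchmark | Ratio | Effect of horizon alone (relative to 0.90%) |
|---|---|---|
| 0.90% | 1.56 | 1.00 |
| 0.78% | 1.80 | 0.90 / 0.78 = 1.15 |
| 0.72% | 1.95 | 0.90 / 0.72 = 1.25 |

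In absolute terms the benchmark is overstated by at most 0.90 − 0.72 = 0.18 percentage points.

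**5. Lower-limit rule.** Exact lower limits at n = 212:

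| Cases | One-sided 95% | Two-sided 95% (as in Table 1) |
|---|---|---|
| 4 | 0.647% | 0.52% |
| 5 | 0.934% | 0.770% |
| 6 | 1.24% | 1.05% |

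- One-sided: four cases exclude neither 0.72% nor 0.90%, and five exclude both. The count is five at either end of the range.
- Two-sided: six cases are needed at 0.90% and still six at 0.78%. Five suffice only if the benchmark is below 0.770%, that is, if fewer than 0.770 / 0.90 = 85.6% of the one-year cases fall by month 6. With exactly 80% by month 3, fewer than (85.6 − 80) / 20 = 28% of the remaining cases could then fall in months 4 to 6, against 33% under an even spread.
- If that shift did apply, the chance of rejection at a true risk of 1.8% (twice 0.9%) would be 33.5% with five cases required and 18.5% with six.

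**The case against.** The strongest reply is that the effect is small and that the protocol contains the facts that bound it. With more than 80% of historic cases in the first three months, fewer than 20% can fall later, and only those after month 6 matter. The floor of 0.72% also needs exactly 80% by month 3 and an empty second quarter, which fits poorly with risk concentrated early. The 1.4% upper limit is an absolute six-month risk that does not depend on the benchmark. The DSMB review described under Safety Monitoring applies no numeric historic threshold. The protocol makes no claim of full equivalence, and its six-month scope is visible in Hypothesis 1.

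All of this stands, and it limits the point to the ratio and, marginally, the lower-limit rule. It does not remove the mismatch: the ratio is still read against a one-year figure, and the direction of the error is known.

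A reader might infer that the mismatch makes excess risk materially harder to detect. The documents do not support that. The lower limit is to come from a formula like that for the one-sided upper limit, and on one-sided limits five cases are needed throughout the range. On two-sided limits the count changes only if historic cases were sparser in months 4 to 6 than an even spread would give.

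**Conclusion.** The point holds, with a bounded size. The horizon mismatch understates the excess-risk ratio by at most a factor of 1.25, and by about 1.15 under the assumed even spread. Against a six-month benchmark the zero-case limit is 1.56 to 1.95 times the historic risk, or about 1.80 under the even spread.

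It would be wrong to put the whole gap between 1.4 and 1.95 down to follow-up length. The step from 1.4 to 1.56 comes from using about 1% instead of 0.9%; only the step from 1.56 upward is due to the horizon. Nor is 1.95 an expected value, since it sits at the extreme floor.

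The range assumes that the share of cases by month 3 can be applied directly to the one-year risk. The documents do not give the six-month historic figure, so only a range can be stated.

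**What to change.** In Risk of Agranulocytosis - Analysis and Power, and where Aim 3 and Hypothesis 1 refer to the literature rate:

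1. Name one benchmark with its time horizon. If the cited cohort report gives cumulative incidence at six months, use it for both the ratio and the lower-limit rule. The documents do not show that it does.
2. Otherwise present both at 0.72% and 0.90%, and say how the range was obtained.
3. Replace the stated ratio of about 1.4 with 1.56 to 1.95, which also removes the discrepancy between 1% and 0.9%.
4. State that the comparison does not cover risk after month 6.

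The cost is SAP wording and a less favourable stated ratio. No change to sample size, visits or follow-up is needed.
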